Exclusion criteria	
 1. Inpatient status 2. Active Congestive Heart Failure Exacerbation 3. Untreated ischemic heart disease 4. Acute exacerbation of respiratory disorders, including COPD and asthma 5. Emergent procedures 6. Pregnancy 7. Previous enrollment in this study 8. Inability to provide informed consent 9. Additional medical testing planned for the same day 10. History of allergic reaction to Propofol 11. Tracheostomy 12. Supra-glottic or sub-glottic tumor 13. Gastrointestinal tract obstruction or delayed transit (including delayed gastric emptying, gastric bezoar, achalasia, toxic megacolon). 14. Prisoners 15. Unable to fit SuperNoVa
Study Procedures	
Pretreatment Evaluation	Candidates will be assessed if the SuperNova fit is difficult or impossible
On-Study Visits	N/A
Follow-up Visits	N/A
End of Study Visit	Subjects will be assessed in PACU before he or she is discharged
Brief Analysis Plan	
Based on the literature, the elapsed time from anesthesia induction to the first airway intervention was 19 ± 10 min in the Mask group ($n=63$) vs. 10 ± 12 min in the Control group ($n=73$, $P < 0.001$)¹⁵. For sample size calculation we used the standard sample size calculation equation¹⁶:
 $n = \frac{2(Z_{\alpha} + Z_{1-\beta})^2 \sigma^2}{\Delta^2}$ 
σ = variation of the measurement Δ = difference to be detected
 
σ and Δ are based on the outcome values from previous publication.¹⁵ This publication showed a time difference (Δ) of 9 minutes with a standard deviation (σ) of ± 10 minutes in both intervention groups. To be able to detect an even smaller time difference of 5 minutes and with a standard deviation of 10 minutes and a drop of percentage of 20% ($\alpha = 0,05$ and $1-\beta = 0,80$) we calculated $n_1=n_2= 75$. A total of 150 patients will be enrolled.

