10. SAMPLE SIZE DETERMINATION AND DATA ANALYSIS

10.1 Sample Size Determination

For sample size calculation we used the standard sample size calculation equation¹⁶:

$$n = \frac{2(Z_{\alpha} + Z_{1-\beta})^2\sigma^2}{\Delta^2}$$

σ = variation of the measurement

Δ = difference to be detected

σ and Δ are based on the outcome values from previous publication.¹⁵

This publication showed a time difference (Δ) of 9 minutes with a standard deviation (σ) of ± 10 minutes in both intervention groups.

To be able to detect an even smaller time difference of 5 minutes and with a standard deviation of 10 minutes and a drop of percentage of 20% ($\alpha = 0,05$ and $1-\beta = 0,80$) we calculated $n_1=n_2= 75$. A total of 150 patients will be enrolled.

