4.1. Randomization

A random number generator program will be used to assign sequential qualified study cases to control group (N = 69) or SuperNO₂VA™EtCO₂ group (N = 69) before collection of additional demographic information and before anesthetic and surgical care. After study group assignment, baseline data will be collected, including age, gender, height, weight, and BMI.

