4.2. Planned Statistical Analysis

Although randomization into treatment groups should minimize differences between the groups, basic bivariate analyses will be performed to determine if there are any clinical or demographic differences, using the data collected in table 1. Logistic regression models will be performed to determine if there are significant differences between the groups for both incidence and severity. Student's t-tests will be performed to determine if there is a significant difference between groups for duration, with Wilcoxon non-parametric tests being performed if the data are non-linear. If significant differences in clinical or demographics characteristics were found, multivariable models will be performed to adjust for these possible confounding variables using logistic regression and ANCOVA models (with GEE models being used to model non-linear data with the appropriate exponential family distribution). All analytic assumptions will be verified and all analyses performed with SAS v9.4, SAS Institute, Cary, NC), analyzing the data as both per-protocol and intention-to-treat.

A Data Safety and Monitoring Board (DSMB) will be convened once half the necessary study population has been enrolled, to discuss the current status of primary endpoints and adverse events, all of which will be tabulated throughout the study. If effect sizes are larger than originally planned and there is a statistically significant decrease in the primary event at this halfway mark, the study will end at this time.

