Protocol Deviations (PDs) will be documented on a Protocol Deviation Case Report Form. PDs are reportable to the institution's governing IRB and regulatory agencies during the annual reporting process, unless otherwise directed by the individual governing IRB requirements or as the specific circumstance dictates. Every attempt shall be made to adhere to the study protocol. However, should an Investigator be required to deviate from the protocol to protect the life or physical well-being of a study subject in an emergent circumstance, such notice shall be given to the study Sponsor as soon as possible, but no more than 5 working days from the date the event occurred. With the exception of an emergent circumstance, prior approval from Sponsor and the appropriate regulatory authorities is required for any change in, or deviation from, the study protocol as such changes may affect the soundness of the investigation or the rights, safety, and welfare of study subjects.

Data Safety Monitoring

Anesthesiologist ([name], MD.), who is not a part of the study, will review adverse events, serious adverse and protocol deviations at the Lyndon B Johnson Hospital (Harris Health) site. These events and deviations will also be reported to the McGovern Medical School IRB as required. They will review all serious adverse events within 24 hours of their occurrence. Once 62 participants have been randomized, an interim analysis will be completed to review efficacy of primary endpoint, adverse events, serious adverse and protocol deviations. A final safety review will be performed once all the subjects complete the study.

Investigator Reports and Responsibilities

Investigators are responsible for ensuring the investigation is conducted in accordance with the study protocol and applicable Federal regulations (21 CFR, Part 812, Subpart E).

Investigators are also responsible for:

- Obtaining IRB approval for study conduct and re-approval as applicable (if more than one Investigator is participating in the study at a site, the Principal Investigator shall be responsible for the IRB approval and re- approvals)
- Obtaining informed consent of study subjects prior to enrollment into the clinical study
- Protecting the subject rights, safety, and welfare

- Maintenance of subject records and confidentiality
- Record retention as defined in Federal regulations 21 CFR, Part 812.140 (a), (d), and (e)

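### The interim efficacy stop has no significance level or final correction, conflicting timing and oversight, and a trigger that does not fit the time endpoint, so the 0.05 error rate is not shown to be held

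*Combined protocol and SAP*

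**What the plan says.** The stopping rule is in section 4.2, Planned Statistical Analysis. On timing and body: "A Data Safety and Monitoring Board (DSMB) will be convened once half the necessary study population has been enrolled". On the trigger: "If effect sizes are larger than originally planned and there is a statistically significant decrease in the primary event at this halfway mark". If both conditions are met, the study ends at that point.

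The Data Safety Monitoring text under Data Monitoring describes the look differently. An anesthesiologist "who is not a part of the study, will review adverse events, serious adverse and protocol deviations", and then: "Once 62 participants have been randomized, an interim analysis will be completed to review efficacy of primary endpoint". It does not say who runs that analysis or whether it can stop the trial.

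Three other places bear on the rule:

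- **Section 10.1, Sample Size Determination.** It reports a 9-minute difference from an earlier publication, then sizes the trial for less: "To be able to detect an even smaller time difference of 5 minutes and with a standard deviation of 10 minutes", with alpha 0.05, power 0.80 and 20% dropout. The total is given as "A total of 150 patients will be enrolled".
- **Section 4.1, Randomization.** It uses another size: "assign sequential qualified study cases to control group (N = 69"), with the same number in the device arm, so 138 in total.
- **Summary Table.** The primary outcome is the elapsed time from induction to the first airway intervention. The Brief Analysis Plan gives the source data as 19 ± 10 min with the mask and "10 ± 12 min in the Control group".

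**The concern.** A rule that ends the trial on a significant interim result gives the primary hypothesis two chances to be declared positive. Without an interim level and a matching final level, the overall error rate exceeds the nominal one unless some other part of the rule prevents it. The only candidate is the requirement that the effect exceed the planned one, and that effect is not defined.

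The rule also cannot be carried out as written. Staff cannot tell when to look, who decides, or what result on the time endpoint stops enrolment: benefit is a longer time, and the rule asks for a decrease in an event. If these choices are made after unblinded data are in hand, the primary conclusion depends on them. A trial stopped this way would also tend to overstate the benefit.

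**Working it through.** **1. The plan's own sample size.** Inputs from section 10.1: difference 5, SD 10, alpha 0.05, power 0.80.

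n per arm = 2 × (1.960 + 0.842)² × 10² / 5² = 62.79

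Multiplied by 1.2 for dropout this is 75.3, which matches the stated 75 per arm. A one-sided 0.05 test would give 50 per arm, then 60 to 63 after dropout, which does not match. The design is therefore a fixed-sample, two-sided 0.05 test with no allowance for a second look.

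**2. Timing.** Half of 150 is 75 and half of 138 is 69. The figure 62 is 41.3% of 150 and 44.9% of 138. It is close to half of the pre-dropout total (2 × 62.79 = 125.6, half 62.8), so a single look may have been intended, but no section says so.

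**3. Interim threshold on the 5-minute reading.** With n patients at the look in two equal arms, SE = SD × √(4/n). The trial stops when Z exceeds the larger of 1.96 and 5/SE.

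**4. Overall error rate.** The interim and final Z are bivariate normal with correlation √(n/N). The final test rejects at |Z| > 1.96.

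| Look / total | SD | SE (min) | 5/SE | Stop at Z > | Stop for benefit only | Stop in either direction |
|---|---|---|---|---|---|---|
| 75/150 | 10 | 2.309 | 2.165 | 2.165 | 5.9% | 6.8% |
| 69/138 | 10 | 2.408 | 2.077 | 2.077 | 6.2% | 7.4% |
| 62/150 | 10 | 2.540 | 1.969 | 1.969 | 6.8% | 8.5% |
| 60/120 (20% dropout) | 10 | 2.582 | 1.936 | 1.96 | 6.7% | 8.3% |
| 75/150 | 11.12 | 2.568 | 1.947 | 1.96 | 6.7% | 8.3% |
| 62/150 | 11.12 | 2.824 | 1.770 | 1.96 | 6.8% | 8.6% |

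The SD of 11.12 pools the source SDs and group sizes (63 and 73) in the Brief Analysis Plan: √((62×100 + 72×144)/134). In the last three rows the 5-minute clause falls below 1.96 and adds nothing.

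**5. The 9-minute reading.** With SD 10, 9/SE is 3.90 at 75 and 3.54 at 62, and the overall rate is 5.0% to 5.1%. With SD 11.12 it is also 5.0% to 5.1%.

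**6. Estimate after an early stop, true difference 5 minutes, SD 10.** On the 5-minute reading with a look at 75, the trial stops when the estimate exceeds 5, so the stopping probability is 50%. With k the threshold Z minus 5/SE, the mean estimate given a stop is 5 + SE × φ(k)/(1 − Φ(k)). At 75, k = 0 and the mean is 5 + 2.309 × 0.798 = 6.84. At 62, k is also 0 and the mean is 5 + 2.540 × 0.798 = 7.03. The overstatement is about 37% to 41%.

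**7. A boundary that holds 0.05.** Lan-DeMets spending of O'Brien-Fleming type gives Z bounds of 2.963 and 1.969 at 50% information (two-sided p 0.0031, then 0.0490). At 62/150 the bounds are 3.296 and 1.963 (p 0.0010, then 0.0497).

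**The case against.** The strongest reply is that the effect-size clause already limits the damage. If the planned effect is the published 9 minutes, alpha is essentially held. Even at 5 minutes, with the plan's own 150, SD 10 and a look at 75, the excess is 0.9 points. At that look significance alone needs about 4.5 minutes (1.96 × 2.309), so the clause does bind: it lowers the benefit-only rate from 6.66% to 5.91%, removing about 45% of the excess. This stands for that case. It does not stand at 62, where significance alone needs 4.98 minutes, nor with 20% dropout or the source SDs. Nor does the plan say which effect or which look applies.

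The either-direction rates can also be challenged, because the rule names one direction. That is fair. They show only what follows if a significant result against the device also stopped the trial, and the conclusion rests on the benefit-only column.

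On oversight, the stopping rule itself is tied only to the DSMB. The 62-patient sentence names no one and confers no power to stop. The accurate statement is that two arrangements for an interim efficacy review are not reconciled, rather than that two bodies hold the same power.

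Finally, with 120 evaluable patients, power under a corrected boundary is about 78.0%, below the planned 80%. But it is 78.2% with no look at all, so the shortfall comes from dropout and not from the correction.

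**Conclusion.** The concern holds and should be fixed before any interim data are examined. The plan contains a binding efficacy stop with no interim level, no adjusted final level and no definition of the effect to be exceeded. Its timing and oversight are not reconciled, and its trigger is not expressed on the primary endpoint.

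On the 5-minute reading, which is the more natural one because the trial was sized on it, the two-sided error rate is 5.9% to 6.8% when only benefit can stop the trial. On the 9-minute reading it is 5.0% to 5.1%. The plan therefore does not show that 0.05 is held.

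These figures assume normal test statistics with known SD, equal arms, and a nominal two-sided 0.05 criterion at each look. The plan also allows Wilcoxon tests and both per-protocol and intention-to-treat analyses without saying which governs the interim decision.

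**What to change.** Reconcile sections 10.1, 4.1 and 4.2 and the Data Safety Monitoring text to one interim look, at one stated number of evaluable patients, run by one named body. Write the rule on time to first airway intervention, in the direction of benefit. Name the test and analysis set that govern the decision. Define the planned effect or drop that clause.

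Then choose one of two courses:

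- **Keep the efficacy stop.** Use a pre-specified boundary at the actual information fraction. A Lan-DeMets O'Brien-Fleming boundary gives p<0.003 then p<0.049 at 50%, or about p<0.001 then p<0.0497 at 62/150. Pocock or classical O'Brien-Fleming bounds would also hold alpha. Pre-specify a bias-adjusted estimate as well, because a stricter boundary makes early stopping rarer without removing the bias when it happens. At 75/150 and a true 5 minutes, k = 2.963 − 2.165 = 0.798, and the mean estimate given a stop is 5 + 2.309 × 0.290/0.212, about 8.2 minutes.
- **Make the interim safety-only** and delete the efficacy stop. The final test then stays at 0.05.

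The cost is wording only, with no extra patients. With 150 evaluable, a true 5 minutes and SD 10, power is about 86.4% with the boundary, against 86.5% with no look and 87.4% under the uncorrected rule with a look at 75. The chance of stopping early at a true 5 minutes falls from about 50% to about 21% (look at 75) or 9% (look at 62).

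### The interim rule stops only on a large, significant effect and no adjusted estimate is planned: at a true 5 minutes, a stopped trial overstates the effect by about 37% to 42% on average

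*Combined protocol and SAP*

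**What the plan says.** Section 4.2 (Planned Statistical Analysis) convenes a monitoring board when half of the required patients have been enrolled, and ends the study "If effect sizes are larger than originally planned and there is a statistically significant decrease in the primary event at this halfway mark". It gives no interim significance level, boundary or spending function. The analyses it names are t-tests, Wilcoxon tests, logistic regression, ANCOVA and GEE models, run per protocol and by intention to treat. Section 5.2 (Methods) adds Fisher's exact test and leaves other methods to the statistician. Neither section mentions estimation after an early stop.

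Two inputs to the rule are unsettled:

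- **Planned effect.** Section 10.1 has two candidates. The design is built "To be able to detect an even smaller time difference of 5 minutes and with a standard deviation of 10 minutes", but the same section says "This publication showed a time difference (Δ) of 9 minutes".
- **Interim size.** Section 10.1 says "A total of 150 patients will be enrolled", so half is 75. Section 4.1 (Randomization) has 69 per arm, or 138 in all, so half is 69. Section 6 (Data Monitoring) says "Once 62 participants have been randomized, an interim analysis will be completed", with efficacy on the primary endpoint among the items reviewed.

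**The concern.** A trial can stop only if its observed difference clears a bar, and one part of that bar is the planned effect itself. If the truth equals the planned effect, no stopped trial can report the truth or less. The named methods would then give the raw difference, with an interval centred on it, as though the sample size had been fixed in advance.

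This is a separate matter from the type I error of the look. A stricter interim boundary protects the test but raises the bar, so the estimate at a stop is exaggerated at least as much. What is at stake is the size of the delay to first airway intervention that users of the device would take from a stopped trial.

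**Working it through.** **Inputs.** Difference 5 minutes, SD 10, alpha 0.05, power 0.80 and 20% dropout (section 10.1); 9 minutes as the published difference (section 10.1); look at 75, 69 or 62 patients (sections 4.2 with 10.1, 4.2 with 4.1, and 6). Assumed: normal outcome, known SD, 1:1 allocation, all patients at the look evaluable, two-sided test.

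**The plan's own figure.** n = 2(1.96 + 0.84)² × 10² / 5² = 62.8, so 63 per arm. Then 62.8 × 1.2 = 75.3, which agrees with the stated 75. Two-sided alpha is therefore the right reading.

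**Mean difference after a stop.** With m patients per arm at the look, SE = 10√(2/m). The bar is c, the larger of 5 and z × SE. For a true difference θ, with u = (c − θ)/SE:

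- chance of stopping = 1 − Φ(u)
- mean reported difference = θ + SE × φ(u) / (1 − Φ(u))

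At θ = 5:

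| Patients at look | SE | Criterion | Bar | Chance of stopping | Mean after a stop | Overstatement |
|---|---|---|---|---|---|---|
| 75 | 2.31 | nominal, z 1.96 | 5.00 | 0.50 | 6.84 | +37% |
| 69 | 2.41 | nominal, z 1.96 | 5.00 | 0.50 | 6.92 | +38% |
| 62 | 2.54 | nominal, z 1.96 | 5.00 | 0.50 | 7.03 | +41% |
| 62 | 2.54 | nominal, t on 60 df | 5.08 | 0.49 | 7.08 | +42% |
| 75 | 2.31 | O'Brien-Fleming, z 2.797 | 6.46 | 0.26 | 7.86 | +57% |
| 62 | 2.54 | O'Brien-Fleming, z 2.797 | 7.10 | 0.20 | 8.53 | +71% |

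First row in full: u = 0, so the mean is 5 + 2.31 × 0.3989/0.5 = 6.84. A Pocock boundary (z 2.178) gives +37% to +48%. Both boundary constants are those for a look at half the information.

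**Other true differences (5-minute bar, nominal significance).**

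- True 3: +109% to +117%, stopping about 20% of the time.
- True 6: +21% to +25%.
- True 7: +11% to +14%.
- True 9: +2% to +4%, or +6.5% to +11% with O'Brien-Fleming.

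**If the planned effect means 9 minutes.** At a true 5, +99% to +102%, but stopping only 4% to 6% of the time. At a true 9, +20% to +23%.

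**Averaged over stopped and continued trials.** With n per arm at the end, the mean estimate is θ + (1 − m/n) × SE × φ(u). At θ = 5:

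- 75 of 150: 5 + 0.5 × 2.31 × 0.399 = 5.46 (+9%)
- 62 of 150: 5 + 0.587 × 2.54 × 0.399 = 5.59 to 5.60 (+12%)

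**Intervals.** At a true 5 and nominal significance, the raw 95% interval misses in 0.025/0.50 = 5% of stopped trials, always upward. With O'Brien-Fleming the miss rate is 0.025/0.264 to 0.025/0.204, so coverage given a stop is about 88% to 91%.

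**What an adjustment achieves.** The Whitehead estimate solves θ + (1 − m/n) × SE × φ((c − θ)/SE) = observed difference. With 75 of 150, an observed 6.84 becomes about 6.46, since 6.46 + 0.5 × 2.31 × 0.327 = 6.84. Simulated over stopped trials at a true 5 and nominal significance, the mean falls from 6.84–7.03 to about 6.5–6.6. The root mean squared error falls from 2.31 to about 2.1 (75 patients) and from 2.54 to about 2.3 (62 patients). At a true 9 it rises slightly, by about 0.1 to 0.2.

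**The case against.** Several points on the other side are sound.

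- **A general figure of 40% or more.** A reader might infer that any stopped trial overstates its effect by at least 40%, whatever the boundary. The documents do not support that. The figure needs a true difference of about 5 minutes or less at nominal significance, and section 10.1 presents 5 minutes as smaller than the published result. At 9 minutes the overstatement is slight. With 75 patients even the 5-minute case gives 37%.
- **Conditional on stopping.** At a true 5 minutes about half of trials would stop, and over all trials the excess is 9% to 12%. This is correct. The conditional figure still matters, because a reader of a stopped trial sees only the stopped result.
- **The size condition as the cause.** A reader might infer that deleting it would cure the bias. With 62 patients, significance alone already needs 4.98 minutes (z) or 5.08 (t), so deletion changes almost nothing. With 75 it lowers the overstatement only from +37% to about +31%, and raises the chance of stopping from 0.50 to 0.58. Most of the bias comes from stopping on a favourable result at all.
- **Scale.** The rule speaks of a decrease in an event, while the primary outcome is a time expected to lengthen. The rule may concern incidence. The minutes above are then illustrative, though selection acts the same way on another scale.
- **Latitude.** Section 5.2 lets the statistician add methods. That permits an adjustment but commits to none.
- **Interim size.** Sixty-two is close to half of 2 × 63 = 126, the total before the dropout allowance. The documents do not say that this was meant.

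**Conclusion.** The point holds in conditional form. If the true difference is the planned 5 minutes with SD 10, a trial stopped under section 4.2 would overstate it on average by about 37% (75 patients) to 42% (62 patients) at nominal significance, and by 57% to 71% with an O'Brien-Fleming boundary. An alpha boundary alone leaves the bias unchanged or increases it.

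Smaller true effects make it worse and larger ones make it mild. The figures rest on the normal approximation, a known SD and a 5-minute bar. An SD of 12, as the summary table reports for the cited trial's control arm, raises the nominal range to about 50% to 62%.

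This does not invalidate the design. It is a gap in the reporting plan that is cheap to close, and one that must be closed before the look to be credible.

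**What to change.** In section 4.2:

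1. State which effect the stopping rule uses, 5 or 9 minutes, and on what scale.
2. Reconcile the interim size with section 6 (Data Monitoring), and state the boundary.
3. Add that, after an early stop, the raw difference is reported together with a bias-adjusted estimate and an interval that account for the stopping rule, for example the Whitehead bias-adjusted mean. Name the interval method too.

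Two alternatives should not be relied on:

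- **Conditional maximum likelihood as the headline.** It diverges near the bar. With 62 patients and a bar of 5.08, an observed 6.0 returns about −0.3 and an observed 5.5 about −9.5. At a true 5, about 28% to 36% of stopped trials would report a negative effect.
- **A stage-wise median-unbiased estimate.** At a first-look stop, the only results counted as more extreme are larger differences at that look, so the estimate equals the raw one.

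Deleting the size condition should not be offered as a remedy for the bias.

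The cost is SAP wording and a little more analysis work, with no extra patients. The downside is a smaller reported effect after a stop. The adjustment is partial: at a true 5 minutes and nominal significance, a mean of 6.5 to 6.6 is still about 30% to 32% too high.
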